Outcome data will be examined for homogeneity of variance, and if necessary transformed to meet this criterion. As this is a within-subjects design, repeated measures analysis of covariance (ANCOVA) will be used to analyze the primary outcome, with drug condition as the within-subjects factor. Similarly, for secondary outcome measures, repeated measured ANCOVA will also be used. A probability level of 0.05 or lower will be considered significant.

As for the neuroimaging data, we will use AFNI software to analyze our data. As a first step we will preprocess the data to correct for motion and then realign the functional volumes to the anatomical volumes. Subsequently, we will perform a regression analyses. Voxels are considered active if the total variance accounted for by the best-fit combination of the regressors of interest will exceed a chosen F ratio ($P = 0.05$ per voxel, uncorrected for multiple comparisons). We will also perform a subtraction analyses between different BOLD responses. To create the average activation maps, we will perform a random effect approach (activation amplitude and t -values will be averaged in each voxel in standardized space across subjects). Group maps will thresholded using 3dClustSim (an analysis module within AFNI). A cluster size of at least 5 voxels will be determined by Monte Carlo simulation.

2. Power analysis

We chose an effect size $d_z = 0.4$ which is consistent with effect sizes of cue reactivity observed for other medications like naltrexone, acamprosate and topiramate. Considering the following parameters: $d_z = 0.4$, α err prob = .05, and power ($1 - \beta$ err prob) = .80, a sample size of 41 subjects will be needed. For fMRI, our sample size of $n=27$ is based on the study by Hariri and colleagues (Hariri et al. 2002) , who used the same task in an fMRI study (between subjects design) with a similar sample size subjects.

3. Accrual number

Consistent with the within-subject design, our previous protocol testing the same study medication (14-AA-0042), the inpatient setting and other human laboratory studies performed in our Clinical Program at NIAAA, we anticipate that

approximately 25% of the enrolled participants may not complete the study. Therefore, we anticipate to enroll up to 55 subjects in order to reach at least 41 completers to satisfy the primary aim

I. Human subjects' protection plan

1. Consent documents and process

Procedures conducted before obtaining consent for this protocol

Screening: subjects are prescreened by phone and then screened in-person through the NIAAA Screening protocol 14-AA-0181, which will provide the necessary data to determine eligibility to this protocol.

Clearance for eligibility: inclusion/exclusion criteria will be reviewed by a team of three individuals: research coordinator (or designee); a registered nurse or nurse practitioner; and PI or AI designated by the PI. All three signatures will be required in order to establish participants' eligibility to this protocol.

Consent procedures

Eligible subjects are enrolled in this protocol after the study-specific consent form for this protocol is obtained. Study investigators designated in the "Qualifications of Investigators" section below will obtain informed consents for the studies of this protocol. All participants will receive a verbal explanation in terms suited to their comprehension of the purposes, procedures and potential risks of the study and of their rights as research participants. Participants will have the opportunity to carefully review the written consent form and ask questions regarding this study prior to signing. Participants will be asked to sign and date the informed consent. A copy of the signed and dated consent will be given to each participant. As part of the consent procedure, participants' ability to understand the consent will be evaluated using the 'NIDA/NIAAA Evaluation of Potential Research Participants' Ability to Consent'. Subjects must answer all questions correctly to proceed with consent signing.

2. Qualifications of Investigators

[name]., Ph.D., M.Sc., is a Senior Investigator at NIAAA and NIDA and Chief of the Section of Psychoneuroendocrinology and Neuropsychopharmacology (CPN). He has several years of clinical and academic experience in the field of addiction medicine. He has extensive experience in direct patient care, and direction and execution of clinical trials. Before joining NIH, he was Core Faculty at the Brown University Medical School. There, he conducted pharmacotherapy human laboratory studies funded by NIH and Foundations at the Brown University Center for Alcohol and Addiction Studies, where he still holds an adjunct position as Associate [name]. [name] is the PI of this study and will be responsible for the conduct, analysis and publication of the results of the study. He will obtain consent for this study.

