Shift in attributions question (modified from Schechter et al. (2006)) measures shifts in attitudes toward alcohol: *“Tell me 5 words or short phrases (adjectives) that describe how you think alcohol affects you.”*

We hypothesize that video feedback in conjunction with motivational interviewing and self-modeling, then, has the potential to help patients to shift motivations and behaviors towards alcohol, as well as maintain abstinence or reduce alcohol drinking, over time.

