11.2 Overview of the Procedure

During this outpatient phase, patients will come into the NIAAA Outpatient Clinic at the NIH Clinical Center for 8 visits and there will be two phases: 4 visits of motivational interviewing sessions with video feedback and 4 visits of supportive counseling, using a crossover design with the order of the two phases counterbalanced across participants. All counseling sessions will be conducted by a physician, nurse practitioner, nurse or masters level counselor.

Motivational Interviewing with Video feedback Phase

Motivational interviewing sessions will be conducted at the initial visit and at alternating visits thereafter with video feedback of these sessions during the intervening weeks. During the videotaped motivational interviewing session, the patient and clinician will discuss in progression the following topics:

- Reasons for abstinence
- Triggers and the patient's reactions (physical, mental) to them
- Reasons for abstinence having just discussed their triggers
- Description of a time when the patient refused alcohol
- Reasons for abstinence having just discussed a time when they had successfully refused alcohol

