We start the conversation with a discussion about the reasons for abstinence to gain insight into why they want to stop drinking prior to making them conscious of how they react to alcohol and how they have tried to avoid it in the present or the past. The second portion of the discussion is a dialogue about the patient's triggers and responses to them. We included this question to instigate a conversation that will help us understand how a patient's motivation shifts when presented with triggers. Following a conversation about the triggers, we return to a discussion about the patient's motivation for abstinence. We chose to include a discussion about a patient's drive to abstain from alcohol after discussing triggers to see whether or not conversations about experiences with alcohol, or people and objects that remind them of alcohol, causes any variation in the way patients discuss their motivation. The fourth portion of our conversation on motivation for abstinence will discuss how patients have successfully coped with triggers and situations where alcohol was present. This portion of the conversation serves two purposes: to help patients understand how pre-existing and developed behaviors have laid the foundation for successful abstinence, and to give them a chance to reflect on the experience of refusing alcohol. Lastly, we end with a discussion of a patient's motivation for abstinence, to evaluate the impact discussions of successful abstinence when faced with alcohol or alcohol-related stimuli may have on a patient's reasons for motivation or self-reported motivation levels. The session should take 30-45 minutes to complete. Between video-taping and motivational interviewing sessions, the clinician will review the video-tape for clips that represent positive motivations, negative motivations, strong reactions to triggers, and opportunities to present models of successful behavior for the patient to try and emulate.

Visits 1 and 3: At Visit 1, the subject will complete the following questionnaires at baseline:

- Motivation to change (SOCRATES) (Miller & Tonigan, 1996)
- Situational Motivation Scale (SIMS) (Guay et al., 2000)
- Hanil Alcohol Insight Scale (HAIS) (Kim et al., 1998)
- Beck Cognitive Insight Scale (Beck et al., 2004), modified
- Attributions towards alcohol (modified WMCI question) (Schechter et al., 2006)
- Mindful Attention Awareness Scale (Brown and Ryan, 2003)
- Curiosity and Exploration Inventory-II (Kashdan et al., 2009)

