- University Rhode Island Change Assessment Scale (URICA) (DiClemente & Hughes, 1990)
- Meta-cognition tasks: Meta-cognition, an individual's ability to comprehend and be mindful of their thought process, is thought to be disrupted in individuals that abuse substances (Goldstein et al., 2009). One task will measure an individual's sense of agency (the amount an individual feels they are the cause of actions around them).

The other task will measure individual's perceptual meta-cognition abilities, or how well they believe they can discriminate between two stimuli.

1. Agency Task: The agency task was designed to assess individual's sense of control (Metcalf et al., 2007). Individuals will use a computer mouse to "catch" falling stimuli (Xs or Os) that are randomly distributed across the screen by moving a small box across a horizontal track. Individuals will then be assessed on their subjective feelings of control over the small box and performance on the task. Turbulence of the mouse, speed of the scroll, and density of targeted stimuli will vary across the 24 trials conducted. This allows us to collect both subjective (self-reported control and performance) and objective (turbulence of the mouse and actual performance) to compare an individual's ability to think about their performance and agency.
2. Flemings Dots Task: The Fleming Dots task was developed to assess perceptive meta-cognition. Two circles will appear on the computer screen containing varied number of dots. After the two circles disappear, individuals undergo a forced choice paradigm, in which they choose the circle that contained the most dots. The difference in dots between the two circles is titrated so that after two continuous correct answers the difference in the number of dots between the two circles decreases, and after one incorrect answer the difference in the number of dots increases. This is done so that the difficulty of the task is equal between participants (Fleming et al., 2010). Individuals are then asked to rate how confident they feel about their answer.

Then the patient will undergo a motivational interviewing session as described above. For Visit 3, a videotaped motivational interviewing session only will be done.

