After the feedback session, patients will fill out the following questionnaires to assess changes in motivation, insight, cognitive insight, and attributions towards alcohol at intervals throughout the experiment: SOCRATES, SIMS, HAIS, modified Beck Cognitive Insight Scale (modified), the modified WMCI question, the Mindful Attention Awareness Scale, the Curiosity and Exploration Inventory-II, the URICA and Metacognition Tasks: Agency Task and the Flemings Dots Task.

Supportive Counseling Phase

The 4 visits of supportive therapy will consist of outpatient visits with supportive counseling sessions lasting approximately the same duration as the motivational interviewing sessions. In addition, the questionnaires: SOCRATES, SIMS, HAIS, modified Beck Cognitive Insight Scale, Mindful Attention Awareness Scale, the Curiosity and Exploration Inventory-II, URICA and the Meta-cognition tasks: Agency Task and Flemings Dots Task will be completed after sessions on Visits 2 and 4 of this phase.

F. Inclusion and Exclusion Criteria

a. Description of study population

This study will enroll individuals with AUD who are treatment- or non-treatment-seeking. The following inclusion/exclusion criteria will be assessed via the NIAAA Screening Protocol 14-AA-0181:

b. Inclusion criteria

1. Male or female individuals 18-70 years old (inclusive)
2. Current Alcohol Use Disorder (AUD) by DSM-5 criteria based on the SCID
3. Most recent urine drug test for illegal drugs of abuse is negative
4. Most recent Clinical Institute Withdrawal Assessment for Alcohol – revised (CIWA-Ar) score is ≤ 8
5. Heart rate ≤ 100 on two separate measurements, both assessed after CIWA-Ar score is ≤ 8
6. Female subjects must be of non-childbearing potential as defined by at least one of the following criteria:

a) Females 45 –70 years old, who are menopausal, defined as follow:

i) Females who are between 45 – 55 years old: they will be considered menopausal if they satisfy all the following three requirements during screening: 1) they are in amenorrhea, defined as absence of menstruation for the previous 12 months; 2) they have a negative urine pregnancy test; and 3) they have a serum FSH level within the laboratory’s reference range for postmenopausal females.

ii) Females who are between 56 – 70 years old: they will be considered menopausal if they are in amenorrhea, defined as absence of menstruation for the previous 12 months before screening.

OR

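### Optional outpatient crossover (tertiary aim): as written, supportive-first participants get no pre-intervention battery, attributions have no supportive-phase comparator, and first relapse allows no within-person contrast

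*Combined protocol and SAP*

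**What the plan says.** Section 11.2 describes four MIVF visits and four supportive counselling visits, "using a crossover design with the order of the two phases counterbalanced across participants". Visits are numbered 1 to 4 within each phase.

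- **MIVF phase.** "Motivational interviewing sessions will be conducted at the initial visit and at alternating visits thereafter", with video feedback in between. "At Visit 1, the subject will complete the following questionnaires at baseline", and the list includes the attribution question. The text continues: "Then the patient will undergo a motivational interviewing session as described above". "For Visit 3, a videotaped motivational interviewing session only will be done". After the feedback sessions at Visits 2 and 4 the battery is repeated, again with the attribution question, "to assess changes in motivation, insight, cognitive insight, and attributions towards alcohol at intervals throughout the experiment".
- **Supportive phase.** The questionnaires and metacognition tasks "will be completed after sessions on Visits 2 and 4 of this phase". No pre-session battery is described, and the attribution question is not in the list.

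Section 11.1 says the attribution question "measures shifts in attitudes toward alcohol". Section D (Tertiary outcome measures) names motivation, time to first relapse and drinking as the outcomes on which MIVF is compared with supportive counselling. Section 11 collects Timeline Follow-Back (TLFB) drinking data at every outpatient visit. Section H gives no analysis for the tertiary aim. Relapse and its time zero are not defined, and no gap between the two phases is stated.

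**The concern.** The measures are introduced as showing changes and shifts, but the schedule is written from the viewpoint of someone who starts with MIVF. A participant who starts with supportive counselling is first assessed after two supportive sessions, and reaches the battery labelled as baseline only after four. A missed pre-intervention measure cannot be recovered.

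Two further gaps sit in the same section. One instrument is collected under only one of the two interventions. One outcome, first relapse, can occur only once per person, so a crossover cannot supply the paired comparison it is designed for.

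The stakes are limited to this aim. Section D says it is meant to guide which behavioural intervention might accompany the drug in a later trial. No primary or secondary conclusion depends on it.

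**Working it through.** The plan states no sample size, power or event count for this aim, so there is no figure to reproduce. The check lays out the schedule and then sizes the loss under stated assumptions.

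**1. Assessments by sequence, counting all eight visits (section 11.2)**

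| Outpatient visit | MIVF first | Supportive first |
|---|---|---|
| 1 | battery before session | none |
| 2 | after session | after session |
| 4 | after session | after session |
| 5 | none | battery before session (MIVF Visit 1) |
| 6 | after session | after session |
| 8 | after session | after session |

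Visits 3 and 7 have none. Each sequence has five batteries. The inpatient schedule (Appendix 2) contains none of these instruments, so it supplies no substitute. In the supportive-first sequence, visit 5 is a valid starting point for change during MIVF. It is not a pre-intervention baseline, and it comes after the supportive assessments at visits 2 and 4.

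**2. Number affected.** Attendance is not stated. With counterbalancing, half of 41 (the completer target in section H) is 20 or 21; half of an assumed 20 is 10.

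**3. Attributions.** Three times under MIVF (Visits 1, 2, 4) and none under supportive counselling, in both sequences.

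**4. Cost of no baseline in a first-phase comparison.** Assume 20 v 21 attending, two-sided 0.05, 80% power and baseline/follow-up correlation ρ. Adjustment multiplies the residual variance by 1 − ρ².

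| ρ | 1 − ρ² | 41 × (1 − ρ²) | Detectable difference |
|---|---|---|---|
| unadjusted | 1 | 41 | 0.90 SD |
| 0.5 | 0.75 | 30.8 | 0.78 SD |
| 0.6 | 0.64 | 26.2 | 0.72 SD |
| 0.7 | 0.51 | 20.9 | 0.64 SD |

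So 41 people unadjusted give the precision of about 31 to 21 people adjusted.

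**5. What the crossover still offers.** A paired comparison of post-session scores in 41 people has 80% power at a standardised paired difference of 0.448. Multiplying by √(2(1 − ρ)), with ρ now an assumed between-phase correlation of 0.5 to 0.7, gives 0.45 to 0.35 SD. This assumes no carryover and needs no baseline.

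**6. First relapse, first phase only.** Assume hazard ratio (HR) 0.5, equal allocation, and 30, 50 or 70% of all 41 relapsing before the switch, so events d = 12.3, 20.5, 28.7. Power ≈ Φ(|ln 0.5| × √(d/4) − 1.96):

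- d = 12.3: Φ(1.215 − 1.96) = 0.23
- d = 20.5: Φ(1.569 − 1.96) = 0.35
- d = 28.7: Φ(1.857 − 1.96) = 0.46

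With 20 attending the values are 0.13, 0.19 and 0.25. If the 30 to 70% refers to the supportive arm only, power with 41 is about 0.17 to 0.40. Those still at risk at the switch number 41 × (1 − 0.3, 0.5, 0.7) = 28.7, 20.5, 12.3.

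**7. Selection into phase 2.** Illustration with gamma frailty, S = (1 + θH)^(−1/θ), θ of 1 to 2, and 20 to 60% of supportive-first participants relapsing in phase 1. The quantity is the phase-2 event-rate ratio, MIVF to supportive.

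- True HR 0.5 in both phases: 0.47 to 0.38.
- Phase-1 HR 0.5, then both groups at the supportive hazard in phase 2: 0.91 to 0.67.
- The same with both at the MIVF hazard, as under full carryover: 0.90 to 0.64.
- No effect in either phase: 1.00.

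Phase-2 relapse can therefore show a difference that does not exist in phase 2, but only when there was an effect in phase 1 and people differ in underlying risk.

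**The case against.** The best defence is that the main contrast needs no baseline. Section D states the aim as MIVF compared with supportive counselling, and both phases collect scores after Visits 2 and 4. On the figures above, the within-person contrast is more sensitive than any first-phase comparison, adjusted or not. This stands. A reader might infer from the missing battery that the outpatient comparison is uninterpretable; the documents do not support that, because post-session scores and TLFB drinking remain comparable.

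It can also be said that the word baseline may mean everyone's first outpatient visit, with the MIVF text simply drafted for those who start there. That is possible, but the heading, the sentence leading into a motivational interview and the supportive schedule all point the other way, and nothing says otherwise. Section 9 allows screening-protocol data to be combined with these; that protocol is not supplied, so the gap is shown for this document only.

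A reader might also treat the visit-5 battery in the supportive-first sequence as a misplaced baseline to be moved or discarded. That goes too far: a pre-MIVF measure has to follow phase 1 when MIVF comes second.

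The missing attribution question may be a drafting slip, since eight other instruments and tasks appear in both lists. In the supportive-first sequence it is asked at visit 5, after four supportive sessions, but that is the next phase's pre-session measure in one sequence only, not a matched comparison. A relapse clock restarted in each phase would be a different endpoint, which the plan does not define.

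**Conclusion.** The point holds as a limited defect in an optional, tertiary part of the study. As written, supportive-first participants, about half of attendees, have no battery before any outpatient session. Attributions cannot be compared between interventions at matched times. First relapse supports only a between-sequence comparison, free of carryover and selection only up to the switch.

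What is lost is change from pre-intervention in one sequence and the precision of a baseline-adjusted first-phase comparison (0.90 SD against 0.78 to 0.64 SD). The first-phase comparison is worth having because no gap between phases is stated, so carryover cannot be ruled out. First-phase relapse power is low, about 0.2 to 0.5 for HR 0.5 with 41 attending.

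Attendance, correlations, relapse shares, HR and frailty are all assumed. The schedule findings depend on none of them, only on reading MIVF Visit 1 as written.

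**What to change.** 1. Give the existing battery before the first session at everyone's first outpatient visit, whichever phase comes first, or say so if that is already meant. Keep the pre-MIVF battery at visit 5 in the supportive-first sequence. Cost: one extra battery there, six instead of five. For symmetry, a pre-session battery at the start of phase 2 may be given in both sequences, making six for everyone.
2. Add the attribution question after supportive Visits 2 and 4. Cost: one question asked twice more per participant.
3. Make the main relapse analysis a first-phase comparison by sequence, censored at the switch, reported as an HR with confidence interval and labelled exploratory. Define relapse and time zero, and say how relapse between discharge and the first outpatient visit (about a week) is counted. Use phase-2 time only as a sensitivity analysis that assumes no carryover and no selection. Cost: a paragraph in section H.

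The title page records the IND as withdrawn in August 2021, and the document does not say whether outpatient visits continue. If they have ended, items 1 and 2 no longer apply. In that case, report how many supportive-first participants lack a pre-intervention battery and compare post-Visit 2 and 4 scores by phase. In that sequence, use the visit-5 battery only as the starting point for change during MIVF, not for change during supportive counselling or from pre-intervention. Item 3 can govern the analysis either way.

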In healthy volunteers, blood ghrelin levels are significantly reduced after acute alcohol consumption (Calissendorff et al., 2005, 2006, 2012; Zimmermann et al., 2007). Additional studies reported that non-abstinent alcoholics had lower blood ghrelin concentration compared to controls (Addolorato et al., 2006; Badaoui et al., 2008; de Timary et al., 2012), and abstinent alcoholics had increased levels (Kim et al., 2005; Kim et al., 2012; Kraus et al., 2005). Together, these studies suggest that ghrelin levels are suppressed by acute alcohol intake and increased during abstinence. The PI, [name], conducted a study that provided the first preliminary evidence of a significant positive correlation between blood ghrelin levels and the Obsessive-Compulsive Drinking Scale (OCDS) craving scores in active drinking alcoholic individuals (Addolorato et al., 2006), a finding also confirmed by another recent study (Koopmann et al., 2012). Subsequent studies partially confirmed the relationship between blood ghrelin levels and alcohol craving in alcoholic individuals, albeit only in those with positive family history of alcoholism (Hillemecher et al., 2007) or in females (Wurst et al., 2007). [name] led the first longitudinal study of serum ghrelin levels in alcoholic patients over the course of 12 weeks treatment. Ghrelin concentrations were assessed at

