baseline (T0; after 72 hours abstinence), then repeatedly at 2 weeks (T1), 6 weeks (T2), and 12 weeks (T3); levels in abstinent patients were compared to those who did not remain abstinent during the 12 weeks treatment. At baseline, blood ghrelin levels were significantly higher in the non-abstinent group ($p=0.035$) and there was a significant *group x time* interaction in ghrelin levels ($F=4.193$, $df=3$, $p=0.012$), [Figure 1 ([name] et al., 2012)]. These findings suggest that ghrelin level in early abstinence predicts later relapse. We also found a significant positive correlation between baseline ghrelin levels and craving during the 12-week period ([name] et al., 2012). In summary, consistent with the preclinical data, human studies show that higher ghrelin levels may be associated with higher craving and alcohol consumption, suggesting that ghrelin is a potential new pharmacological target for AUD. Although only peripheral levels of ghrelin were tested, these results support the hypothesis that ghrelin may influence alcohol craving and consumption via the DA-related rewarding processing. This is consistent with a PET study (although in a different population of obese subjects) showing that peripheral ghrelin levels were inversely associated with the availability of DA type 2 receptor (D2R) in the caudate, putamen, ventral striatum, amygdala, and temporal lobes, i.e., higher ghrelin levels were associated with lower D2R availability, presumably from increased DA release and receptor occupancy (Dunn et al., 2012). Notably, although only peripheral ghrelin levels were tested, circulating ghrelin may reach CNS targets directly by crossing the BBB (Chollet et al., 2009).

[figure not shown]

Figure 1. Differences in blood ghrelin levels between abstinent and non-abstinent alcoholic patients.

Human ghrelin administered intravenously acutely increases alcohol craving: first-in-man preliminary findings

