Overview: During the inpatient phase, eligible participants will undergo Stages 1 and 2, where study drug (PF-05190457 or placebo) administration will be counterbalanced. A study drug wash-out window of at least 2 days will take place between Stage 1 and Stage 2. During each Stage, subjects will take the study drug twice a day (b.i.d.) for a maximum of 14 days in order to allow flexibility, maximize feasibility and minimize scheduling problems. At the end of each Stage, the last evening dose of the study medication will not be administered. As part of this study, subjects will be admitted to the inpatient unit, 1SE and will remain as inpatients for the duration of the two Stages and the wash-out window. During the washout period (i.e., when participant is not receiving the investigational study drug), a participant may request an unaccompanied pass to leave the NIH Clinical Center; the PI, MAI or covering physician will evaluate the pass request and determine whether the pass may be granted during the washout period.

The following research procedures (1-3 listed below) will take place once in Stage 1 and once in Stage 2. These procedures will be the same for Stage 1 and Stage 2.

Physiologic Measures: As part of physiologic monitoring in this study, we are using several biosensors (detailed below) provided by [name] at the Media Laboratory, Massachusetts Institute of Technology. Biosensors can provide comprehensive information of one's internal physiological state by measuring multiple physiological parameters continuously over long time scales. Analysis of this composite data can potentially reveal previously unobservable effects in the context of abstinence, medication administration, for example, compared to monitoring singular measures of physiologic data. These sensors are not considered "new investigational medical devices" since the main thing that is new is not the sensors but the packaging/form factors that allow comfortable recording as well as accompanying technology for communicating, analyzing, and visualizing physiological information.

A Material Transfer Agreement is in place to obtain the Biosensors used in this study.

We will use the following sensor:

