trial provides a controlled baseline that controls for all aspects of stimuli and movement except for the nature of the beverage. After that, another 3-minute relaxation period will follow. Next, participants will undergo a similar procedure with personalized food cues; this will be used given that our preliminary data from 14-AA-0042 show an effect of the study medication on food craving assessed during the CR. Finally, two 3-minute alcohol cue exposure trials that will be identical to the water trial except the glass of water will be replaced with their preferred alcohol beverage and the bottle of water will be replaced with the appropriate commercially-labeled alcohol bottle. Two alcohol trials will be conducted to gain a stable estimate of participants' reactions to alcohol cues and because two exposures have proven most sensitive to differential effects in previous studies (trials will be presented in the same order for all participants because of known carryover effects). After every 3 minutes of beverage exposure, participants will rate their urge to drink alcohol by completing the Alcohol Urge Questionnaire (AUQ) (Bohn et al. 1995) (Appendix 9). The term urge to drink is explained to the subject as "want, desire, craving, thirst for or wish to drink". The AUQ will be complemented by the Alcohol Attention Scale (AAS), which consists of two 10-point Likert-type scales assessing attention to the sight and smell of water and alcohol cues.

2. Functional Magnetic resonance imaging (fMRI) [for those who have no exclusion criteria for fMRI scanning or due to scheduling limitations, e.g. scanner shutdown]

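### The primary crossover model names drug condition as its only factor, so any Stage 1-to-Stage 2 change in craving stays in the error term and costs precision

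*Combined protocol and SAP*

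**What the plan says.** The design is a two-period crossover. Section E (Inpatient phase, Overview) states that "study drug (PF-05190457 or placebo) administration will be counterbalanced" across Stages 1 and 2. The cue-reactivity session, the virtual buffet and the scan each happen once per stage, and "These procedures will be the same for Stage 1 and Stage 2". Participants "will remain as inpatients for the duration of the two Stages and the wash-out window", so Stage 2 always falls later in one continuous admission.

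The primary model is a single sentence in Section H.1: "repeated measures analysis of covariance (ANCOVA) will be used to analyze the primary outcome, with drug condition as the within-subjects factor". Secondary outcomes get the same method; neuroimaging has its own plan in H.1 and is outside this point. No stage, period, sequence or order term is named in H.1 or elsewhere in the text reviewed. The method is called ANCOVA, but no covariate is listed. On significance, H.1 says only "A probability level of 0.05 or lower will be considered significant", without stating whether tests are one- or two-sided.

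**The concern.** Each completer contributes one drug-minus-placebo difference. If craving shifts between stages for reasons unrelated to drug, that shift adds to the difference in one order and subtracts from it in the other. Counterbalancing cancels it in the mean when completers are near-balanced by order. It does not cancel it in the variance, so a model with drug alone treats a systematic, known source of variation as noise.

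A shift is plausible but not shown. The Background states that "ghrelin levels are suppressed by acute alcohol intake and increased during abstinence", and reports "a significant positive correlation between baseline ghrelin levels and craving during the 12-week period". Stage 2 comes after a longer stay on the unit. Neither source reports craving at repeated cue sessions.

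At stake is the width of the interval for the primary effect and the power obtained from 41 completers. Section D says the primary and secondary results will guide whether a Phase 3 trial is run.

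**Working it through.** **Inputs from the documents.** dz = 0.4, alpha = 0.05, power 0.80 and 41 completers (H.2); about 25% non-completion and 55 enrolled (H.3); one cue session per stage (Section E).

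**Assumptions not in the documents.** The size of the stage change; whether the SD behind dz = 0.4 already contains stage variation; sidedness.

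**1. The plan's own figure.** For a paired t-test the noncentrality is 0.4 × √41 = 2.561 on 40 df. One-sided power is 0.809, so 41 reproduces. Two-sided power is 0.705, and 52 completers would be needed for 0.80. Enrolment: 41/0.75 = 54.7, so 55 reproduces.

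**2. Model.** Write D = τ + sπ + e for the drug-minus-placebo difference, with s = +1 in one order and −1 in the other, π the stage change, and SD(e) = 1. The drug-only analysis is a paired t-test on D (40 df). With stage fitted, the drug effect is the unweighted mean of the two order means, with pooled within-order variance (39 df).

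At a 21/20 split the drug-only error variance is inflated by 1 + π² × (41/40) × (1 − 1/41²). At π = 0.5 this is 1 + 0.25 × 1.0244 = 1.256, equivalent to 41/1.256 = 32.6 completers. The width ratio is √1.256 = 1.121, or 1.120 after allowing for the one df that the stage term uses.

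**3. dz = 0.4 on the stage-free SD, split 21/20.** Power is from 400,000 simulated trials per cell and type I error from 200,000. Paired entries are the two directions of the change.

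| Stage change (SD) | 0.1 | 0.25 | 0.5 |
|---|---|---|---|
| Variance inflation | 1.010 | 1.064 | 1.256 |
| Equivalent completers | 40.6 | 38.5 | 32.6 |
| Interval width ratio | 1.004 | 1.031 | 1.120 |
| Two-sided power, drug only | 0.707 / 0.698 | 0.697 / 0.668 | 0.646 / 0.590 |
| One-sided power, drug only | 0.810 / 0.803 | 0.805 / 0.782 | 0.772 / 0.724 |
| Two-sided type I error, drug only | 0.049 | 0.044 | 0.029 |

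With stage fitted, power is 0.703–0.706 two-sided and 0.807–0.809 one-sided throughout, and two-sided type I error is 0.050–0.051.

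**4. dz = 0.4 on an SD that already includes stage variation.** Here SD(e)² = 1 − π²(1 − 1/41²), with the change in units of total SD. Two-sided drug-only power is 0.712/0.701, 0.723/0.698 and 0.758/0.701 at 0.1, 0.25 and 0.5 SD, so it does not fall materially below the 0.705 in step 1. Fitting stage raises it to 0.709, about 0.73 and 0.822. One-sided at 0.5 SD, it goes from 0.862/0.818 to 0.896.

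**5. Unequal orders among completers.** Bias in the drug-only estimate is π × (n₁ − n₂)/41. With 28 and 27 enrolled per order and random 25% loss, the mean absolute imbalance is 6.4%. The mean absolute bias relative to 0.4 is therefore 1.6%, 4.0% and 8.0% at 0.1, 0.25 and 0.5 SD. An imbalance of at least 7/41 (24/17) has probability 0.041. There, a 0.25 SD change gives a bias of 0.25 × 7/41 = 0.043 SD, or 11% of 0.4.

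**6. Cost if there is no stage change.** At 21/20, two-sided power is about 0.71 and one-sided about 0.81 under either model. At 24/17, fitting stage lowers two-sided power from 0.705 to 0.693 and one-sided from 0.808 to 0.798.

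**The case against.** The strongest reply is that H.1 names the within-subjects factor without excluding other terms, and that an ANCOVA presupposes covariates, so stage might be intended. That is possible, but nothing says so. An analyst following the text would fit drug alone, and an unnamed sequence main effect would not remove a stage shift.

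A second reply is that baselines exist. Section E.1 says of the water exposure that the "trial provides a controlled baseline that controls for all aspects of stimuli and movement except for the nature of the beverage". Section E.4 also schedules the urge questionnaire before the first dose of each stage and before each procedure. Used as a covariate or reference score, these could absorb much of a general drift in craving. H.1 does not say that any of them is used, and none would remove a changed response to the alcohol cue itself at the second session.

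Third, no stage effect is documented, and in the approximate schedule in Appendix 2 the cue sessions are only about ten days apart (Day 7 and Day 17). The loss is negligible at 0.1 SD and small at 0.25 SD; most of it comes from the assumed 0.5 SD case. If the reference effect sizes for dz already carry period variation, planned power is not eroded. All of this stands, and it limits the point to a conditional loss of efficiency.

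Validity is also largely safe: the drug-only test is conservative with near-balanced orders, and a large imbalance is unlikely.

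**Conclusion.** The point holds. As written, the primary model leaves any stage change in the error term, although stage and order are known for every participant. On the stage-free SD, the interval is 0.4%, 3% or 12% wider than necessary for a change of 0.1, 0.25 or 0.5 SD. At 0.5 SD, two-sided power falls from about 0.70 to 0.65 or 0.59, and one-sided power from 0.81 to 0.77 or 0.72. If dz = 0.4 already includes stage variation, the plan loses no material power against its own target but forgoes a gain, up to 0.82 two-sided at 0.5 SD.

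These figures rest on an assumed stage change and a 21/20 split. Bias is secondary: small under random attrition and material only with an unusual imbalance by order. The change should be made because it is nearly free, not because the planned test is invalid. Confidence is medium, since the size of any stage change is unknown.

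**What to change.** In H.1, add stage and sequence as fixed effects beside drug in the primary model. In repeated-measures ANCOVA terms, this means sequence as a between-subjects factor plus sequence-by-drug, with the drug effect taken as the unweighted mean over the two sequences. With complete pairs it is the stage term (or sequence-by-drug) that does the work; a sequence main effect alone would not.

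Use the same terms for the virtual buffet outcome. Report completers by order, and state whether the test is one- or two-sided.

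The cost is a sentence or two of wording and 1–2 degrees of freedom. If there is no stage change, power is unchanged at 21/20 and falls by about 1 point at 24/17. This version is dated August 2021, so the change should be recorded before unblinding. If the data are already unblinded, report both models.
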